8.3 Procedures for detecting, evaluating, recording & reporting AEs and SAEs

8.3.1 Detecting AEs and SAEs

All AEs and SAEs meeting the criteria for recording within the PEPPY trial (see section 8.1) are recorded from the time a participant consents to join the trial until the last trial follow-up. The Trial Office and centre staff will ask about the occurrence of relevant AEs/SAEs (i.e. those that meet the criteria for recording within the PEPPY trial) at every appointment, within follow-up questionnaires, ad hoc phone calls and other contact with the participant.

8.3.2 Evaluating AEs and SAEs

When an AE or SAE occurs, it is the responsibility of the local Investigator (or delegate) to review appropriate documentation (e.g. hospital notes, laboratory and diagnostic reports) related to the event.

Assessment of Seriousness

The Investigator must make an assessment of seriousness as defined in Section 8.1.

Assessment of Relatedness (causality)

The local Investigator must make an assessment of whether the AE/SAE is likely to be related to treatment according to the following definitions:

- Related: resulted from administration of the research procedures.
- **Unrelated**: where an event is not considered to be related to the research procedures.

Alternative causes such as natural history of the underlying disease, concomitant therapy, other risk factors and the temporal relationship of the event to the treatment should be considered.

Assessment of Expectedness

Expectedness will be assessed for all AEs and SAEs by the local Investigator.

IRAS ID: 338183 PEPPY protocol version 3.0 26/02/2025 ISRCTN: xxxxxx Page 25 of 51

8.3.3 Recording AEs and SAEs

Adverse events will be recorded in the case report forms (CRFs) or questionnaires. The local Investigator (or delegate) should then record all relevant SAEs on the SAE form.

In addition, death for any cause (related or otherwise) is recorded on the SAE form.

8.3.4 Reporting SAEs

Reporting responsibilities of centres

Once the local Investigator becomes aware that an SAE has occurred in a trial participant, they must report the information to the Trial Office/Chief Investigator within 24 hours of becoming aware of the event as per the Sponsor guidance.

The SAE form must be completed as thoroughly as possible with all available details of the event and signed by the local Investigator or designee. If all the required information is not available at the time of reporting, the Investigator must ensure that any missing or follow-up information is provided as soon as this becomes available. It should be indicated on the report that this information is follow-up information of a previously reported event.

To report an SAE to the Trial Office, centre staff can either complete a hard copy of the SAE form and email it to the Trial Office or upload the SAE onto the trial website. If the SAE form is uploaded onto the trial website, the Trial Manager will be automatically notified.

If, in the opinion of the local PI and/or the CI, the event is confirmed as being serious but not related, or serious, related and expected, expedited reporting to Sponsor is not required. Rather these will be summarised and reported to Sponsor, REC, Funder, TSC and DMEC in their regular progress reports. Only expedited if serious, related and not expected event.

Reporting responsibilities of the Trial Office

The Trial Office will notify the Sponsor within 24 hours of receiving the signed SAE notification if the event is serious, related and not expected.

The sponsor will provide an assessment of the SAE. A Sponsor cannot downgrade an assessment from the local PI or CI. Any disparity will be resolved by further discussion between these parties and documented in the TMF.

8.3.5 Regulatory reporting requirements

The CI or delegate reports any SAEs that are related to trial procedures and not expected to the REC within 15 days of the CI becoming aware of it using the HRA SAE form.

All SAEs are summarised and reported to the Ethics Committee, the Funder, the Trial Steering Committee and the Data Monitoring and Ethics Committee in their regular reports.

8.3.6 Follow up procedures

After initially recording and reporting an SAE, the local Investigator is required to follow each participant as indicated by clinical practice. Follow up information on an SAE should be reported to the Trial Office as described above in the Section on 'Reporting responsibilities of centres'. The Trial Office will notify the Sponsor about any follow-up information.

8.3.7 **Pregnancy**

Pregnancy is not considered an AE or SAE, however if a participant becomes pregnant while participating in the trial, the details of the pregnancy should be reported to the treating clinician and research team as soon as the participant becomes aware and the participant will be

IRAS ID: 338183 PEPPY protocol version 3.0 26/02/2025 **ISRCTN: xxxxxx** Page 26 of 51 withdrawn from the trial and her care will be provided by the centre. Notification of pregnancy during the trial will be reported in the change of status form.

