7.5 Change of Status/Withdrawal procedures

Participants remain in the trial unless they choose to withdraw consent. Participants are free to withdraw from the trial at any timepoint. All changes in status, with the exception of complete withdrawal of consent, mean the participant is still followed up for all trial outcomes wherever possible. All data collected up to the point of complete withdrawal is retained and used in the analysis.

Following informed consent, if a participant loses capacity, the consent given when capable remains legally valid. In such circumstances, identifiable data collected with consent will be retained and used in the study but no further data will be collected or research procedures carried out.

Participants who do not receive their allocated treatment or receive the other (non-allocated) intervention or discontinue their healthcare management are not considered withdrawals and will be followed-up for all trial outcomes unless they request otherwise. One of the outcomes is treatment received. This is a pragmatic study and will monitor accruing data on treatment initiated and continued during the study which will inform the proportion of participants continuing in the two randomised treatment pathways.

Participants who request that no further questionnaires are issued (i.e. completing questionnaires) will be followed up for other trial outcomes unless they are complete withdrawals.

Participants for whom any outcome data are available are included in an intention to treat analysis.

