10. STATISTICAL ANALYSIS

Analyses will be conducted according to a pre-specified Statistical Analysis Plan. All participant characteristics (e.g. age, prolapse severity, parity, BMI, ethnicity) and outcome measure data will be summarised, by group, using the appropriate descriptive statistics: mean and standard deviation for continuous outcomes (or medians and interquartile range for skewed data), and counts and percentages for dichotomous and categorical outcomes.

The main effectiveness analysis will be based on the intention to treat principle. The analysis of the primary outcome measure will estimate the mean difference (with 95% confidence intervals) in the PFDI-20 score at 12 months between the PFMT plus pessary and PFMT alone groups

IRAS ID: 338183 ISRCTN: xxxxxx using a longitudinal ANCOVA model (which assumes incomplete outcome data to be missing at random). The model will incorporate PFDI-20 scores at 6- and 12-month time-points, with age group, baseline prolapse severity and baseline PFDI-20 score as fixed effects and recruitment centre as a random effect. The treatment effect will be estimated from the linear combination of treatment plus time-by-treatment interaction. Missing baseline data will be imputed. The longitudinal ANCOVA model will also estimate mean differences in PFDI-20 at 6 months. Statistical significance will be at the 5% level.

The missing at random assumption for primary outcome data will be assessed further in sensitivity analyses. Treatment effects will be estimated under varying assumptions of data being missing not at random using pattern- mixture models [36]. A complete case analysis will also be conducted.

Given the potential for discontinuation of PFMT and/or pessary use, we will conduct a secondary analysis of compliers to estimate the effect of receiving the intervention as randomised, using complier average causal effect (CACE) estimators [37]. The CACE analysis will take a maximum likelihood approach, which can assume incomplete data to be missing at random, and can be adjusted for covariates. This analysis will provide unbiased effect estimates of receiving PFMT plus pessary (efficacy), which will complement the unbiased intention to treat effect estimates of being offered PFMT plus pessary (effectiveness). An "as treated" analysis will analyse participants on the basis of treatment received (Y/N).

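### Section 8.3.7 withdraws women who become pregnant from the trial, while section 7.5 keeps them in follow-up; the two must be reconciled

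*Protocol*

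**What the plan says.** Protocol section 8.3.7 (Pregnancy) states that pregnancy is not itself an adverse event. It asks that details be passed to the treating clinician and the research team, and then directs that the participant be "withdrawn from the trial and her care will be provided by the centre". It ends: "Notification of pregnancy during the trial will be reported in the change of status form".

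Section 7.5 (Change of Status/Withdrawal procedures) sets the general rule on who leaves the trial:

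- "Participants remain in the trial unless they choose to withdraw consent".
- All changes in status, "with the exception of complete withdrawal of consent, mean the participant is still followed up for all trial outcomes wherever possible".
- Women who do not receive their allocated treatment, receive the other treatment, or "discontinue their healthcare management are not considered withdrawals and will be followed-up for all trial outcomes unless they request otherwise".
- "All data collected up to the point of complete withdrawal is retained and used in the analysis".
- One exception to continued data collection is written out: loss of capacity after consent, when no further data are collected. Section 4.6 repeats it.

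Section 8.3.1 has recordable adverse events collected from consent to the last trial follow-up, through appointments, questionnaires and other contacts. Section 10 states: "The main effectiveness analysis will be based on the intention to treat principle".

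**The concern.** The two sections give different instructions for the same woman. Under 7.5, a woman who becomes pregnant and does not withdraw consent has a change of status and is still sent her questionnaires. Under 8.3.7 she is out of the trial, by a decision that is not hers. Nothing in 8.3.7 limits the withdrawal to the intervention, and nothing in 7.5 exempts pregnancy.

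At stake is follow-up that the trial could have at no extra effort. Pregnancy during the trial is foreseeable: section 4.3 admits women from age 18 and excludes pregnancy only at entry. A woman withdrawn before 6 months would give no follow-up PFDI-20 score, and one withdrawn later would lack the 12-month score, which is the primary endpoint. Her remaining questionnaires and contacts are also a route by which new recordable adverse events are found. Centres could resolve the conflict differently, one stopping all contact and another continuing. An analysis plan cannot recover questionnaires that were never sent, so this has to be settled in the protocol.

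**Working it through.** **1. The provisions side by side**

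| Question | Section 7.5 | Section 8.3.7 |
|---|---|---|
| Who ends participation? | The participant, by withdrawing consent | The protocol, on notification of pregnancy |
| How is the event recorded? | As a change of status | On the change of status form |
| What follows for outcomes? | Follow-up for all outcomes where possible | Withdrawn from the trial, with no follow-up described |
| Is stopping treatment distinguished from stopping follow-up? | Yes | No |
| Written exceptions | Loss of capacity | Not applicable |

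The form named in 8.3.7 belongs to the category for which 7.5 requires continued follow-up. The conflict is therefore in the text and does not depend on any assumption.

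**2. What is lost and what is kept if 8.3.7 is applied literally**

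- Lost: questionnaires and clinical outcomes due after the withdrawal date, and detection of new recordable adverse events after that date.
- Kept: everything collected earlier (section 7.5). Anyone with any outcome data stays in the intention-to-treat analysis, so a woman withdrawn after her 6-month questionnaire still contributes to the longitudinal model in section 10.
- Kept: follow-up of serious adverse events already reported (section 8.3.6).
- Scope: only related adverse events, related serious events and all deaths are recorded in this trial (section 8.2), so the safety loss is confined to new events of those kinds.

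**3. The plan's own sample size (section 9.1)**

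Inputs: difference 12, SD 40, two-sided alpha 0.05, power 90%, loss 15%.

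n per group = 2 × (1.960 + 1.282)² × 40² / 12² = 233.5, rounded up to 234.

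234 / 0.85 = 275.3, rounded up to 276 per group, or 552 in total. The stated figure reproduces.

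Evaluable per group: 276 × 0.85 = 234.6. Power = Φ(12 / (40 × √(2/234.6)) − 1.960) = Φ(3.249 − 1.960) = 90.1%.

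**4. Effect of pregnancy withdrawals on power**

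The documents give neither a pregnancy rate nor an age distribution. The rates below are assumptions, added on top of the 15% loss.

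| Assumed rate | Women of 552 | Evaluable in total | Power |
|---|---|---|---|
| 0% | 0 | 469.2 | 90.1% |
| 0.5% | 2.8 | 466.4 | 90.0% |
| 1% | 5.5 | 463.7 | 89.8% |
| 2% | 11.0 | 458.2 | 89.5% |

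At 2%: 276 × (1 − 0.17) = 229.1 per group, and Φ(12 / (40 × √(2/229.1)) − 1.960) = Φ(3.211 − 1.960) = 89.5%. The largest fall in this range is 90.13 − 89.45 = 0.68 percentage points. If these women are already counted within the 15%, power stays at 90.1%.

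**The case against.** The best defence is that 7.5 is a general rule that already admits an exception. It stops data collection on loss of capacity as well as on withdrawal of consent, so 8.3.7 can be read as a second specific exception kept in its own section, in line with pregnancy being an exclusion at entry. That is a possible intention, but it is not written. Section 7.5 spells out the capacity exception and is silent on pregnancy, and 8.3.7 sends pregnancy to the change of status form without saying that the usual consequence of that form is set aside. At the least, a definition of withdrawal and a cross-reference are missing.

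The defence is right to limit how far the point can be taken. A reader might infer any of three stronger things:

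- **That 8.3.7 breaches the intention-to-treat analysis.** It does not order anyone out of the analysis. Section 7.5 keeps data collected before withdrawal and includes anyone with outcome data. The conflict is over continued follow-up of randomised women.
- **That safety data are discarded.** Nothing collected is discarded, pregnancy details still go to the research team, and serious events already reported are still followed. Only the detection of new recordable events is cut short.
- **That the treatment effect is biased.** The protocol gives no data linking pregnancy to the PFDI-20 score and no reason to expect pregnancies to differ between arms. Section 10 already plans pattern-mixture sensitivity analyses for data missing not at random.

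**Conclusion.** The contradiction is certain and the numerical effect is small. Sections 7.5 and 8.3.7 cannot both be applied as worded to a woman who becomes pregnant and does not withdraw consent. Applying 8.3.7 literally creates missing data after randomisation that 7.5 would avoid. On an assumed 0.5% to 2% of 552 women, power moves by less than one percentage point, or not at all within the 15% allowance. The size rests wholly on that assumed rate; the inconsistency does not. It should be corrected because centres need one rule for whom to follow. The primary result is not at risk.

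**What to change.** Amend 8.3.7 to agree with 7.5 on follow-up. State that pregnancy is a change of status, that questionnaire and adverse-event follow-up continue unless the woman withdraws consent, and that her data are analysed in the group to which she was randomised. This carries the rule already in 7.5 across to 8.3.7. Whether treatment or vaginal examinations continue during pregnancy is a clinical matter for the centre, and this point takes no position on it.

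The cost is one sentence in a protocol amendment, reviewed by the sponsor before application to the ethics committee and R&D as section 15.1 requires. It adds no visits or staff, because the questionnaires are already planned for every participant, and the sample size stays at 552.

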9. SAMPLE SIZE AND PROPOSED RECRUITMENT RATE

9.1 Trial sample size

Five hundred and fifty-two women (276 per group) will be randomised to provide 90% power to detect a difference of 12 points in the PFDI-20 score at 12 months. This allows for a 40% pessary fitting non-success rate, which would potentially reduce the group difference in PFDI-20 from 20 (the upper limit of the minimal clinically important difference [35]) to 12, which remains within the lower limit of 6.2. A standard deviation of 40 is assumed, two-sided alpha of 0.05, and 15% loss to follow-up.

A sample size of 552 also provides power for the analysis of secondary outcomes, e.g. we will have more than 90% power (2-sided test, 5% level of significance) to detect a 20% difference between groups in the proportion of women with a Modified Oxford Scale rating of 2 or less (assuming that at least 50% in the PFMT plus pessary group obtain a score of more than 2 at 12 months).

The number of potentially eligible women (those referred for PFMT for prolapse) reported by participating centres ranged from 7 to 40 per month, median 17. Assuming 70% of women will be eligible and 50% agree to participate, in 13 centres recruiting for an average of 12 months (maximum 18 months with centres starting in a staggered fashion), approximately 900 women could participate, allowing us to cover seasonal variations and other unexpected recruitment issues and still reach our target of 552 randomised participants.

9.2 Progression beyond the pilot

A number of criteria will be considered carefully when deciding upon the feasibility and appropriateness of continuing with the trial, relating to centre and participant recruitment and pessary fitting success (Table 1).

Table 1. Criteria to inform progression from pilot to full trial

| Progression criterion | Red | Amber | Green |
|---|----------|-------------|-----------|
| Recruitment rate is at least 4 women per centre per month (from 3 rd month onwards) | 1 centre | 2-4 centres | 5 centres |
| Number of centres opened during pilot | 1 centre | 2-4 centres | 5 centres |
| Total number of participants recruited during pilot | <20 | 20 to 58 | 59 |
| 4. Pessary fitting success* rate is 60% or greater | 1 centre | 2-4 centres | 5 centres |

^{*}centre confirms with participant 1 week after fitting that the pessary can be successfully and comfortably retained when in situ

One or more criteria at amber would indicate action and review was needed to: improve recruitment methods e.g. based on findings from process evaluation interviews and audiorecordings; increase centre numbers using those centres we have in reserve; increase sample size to compensate for lower than anticipated fitting success rates. One or more criteria at red would reflect a position where the trial could only progress with a very strong recovery plan approved by the funder, and monitored closely to ensure it is effective once in place.

Qualitative data from the process evaluation collected during the internal pilot will be used to identify actions that can be taken to support recruitment (see Sections 7 and 12). A newsletter will be sent to all centres that offers feedback on strategies to increase recruitment and ways to enhance delivery of the intervention in line with trial protocol.

PEPPY protocol version 3.0 26/02/2025 **ISRCTN: xxxxxx** Page 27 of 51

9.3 Recruitment rates

Individualised recruitment targets will be given to centres depending on their recruitment potential and progress, however for planning purposes we have estimated conservatively that centres will randomise 4 women per month from their 3rd month onwards (Figure 2). The Data Monitoring and Ethics Committee (DMEC) will be asked to monitor EDI characteristics within the recruited sample in comparison to norms from the latest census data.

Figure 2. Recruitment projection across 13 centres over 18 months orange denotes number of centres recruiting

To mitigate against poor recruitment, we will:

- 1. Focus first on setting up those centres that have the shortest waiting lists for both PFMT and pessary appointments, those that already have combined PFMT/pessary fitting clinics, and those we know have recruited efficiently in previous trials.
- 2. Use methods which have been successful in our previous trials of conservative management of prolapse [5,6,21]. All trials recruited to target (or beyond) and had excellent retention. In particular, the TOPSY trial [21], involving women with a pessary, had a 97% retention rate at 4-year follow-up. Successful recruitment methods include giving the choice of paper or electronic consent and questionnaire completion, which helps to avoid issues of digital exclusion. For centres there will be monthly centre forums where the team can share recruitment advice with centres and centres can share good practice with their peers.
- 3. Monitor recruitment closely during the pilot phase by reviewing screening logs and asking centres for feedback on any barriers they identify in the recruitment process. We will discuss these findings at PMG meetings, which include our PPI team members, and also seek advice from the TSC as needed to identify additional strategies to overcome these barriers.

10. STATISTICAL ANALYSIS

Analyses will be conducted according to a pre-specified Statistical Analysis Plan. All participant characteristics (e.g. age, prolapse severity, parity, BMI, ethnicity) and outcome measure data will be summarised, by group, using the appropriate descriptive statistics: mean and standard deviation for continuous outcomes (or medians and interquartile range for skewed data), and counts and percentages for dichotomous and categorical outcomes.

The main effectiveness analysis will be based on the intention to treat principle. The analysis of the primary outcome measure will estimate the mean difference (with 95% confidence intervals) in the PFDI-20 score at 12 months between the PFMT plus pessary and PFMT alone groups

IRAS ID: 338183 ISRCTN: xxxxxx using a longitudinal ANCOVA model (which assumes incomplete outcome data to be missing at random). The model will incorporate PFDI-20 scores at 6- and 12-month time-points, with age group, baseline prolapse severity and baseline PFDI-20 score as fixed effects and recruitment centre as a random effect. The treatment effect will be estimated from the linear combination of treatment plus time-by-treatment interaction. Missing baseline data will be imputed. The longitudinal ANCOVA model will also estimate mean differences in PFDI-20 at 6 months. Statistical significance will be at the 5% level.

The missing at random assumption for primary outcome data will be assessed further in sensitivity analyses. Treatment effects will be estimated under varying assumptions of data being missing not at random using pattern- mixture models [36]. A complete case analysis will also be conducted.

Given the potential for discontinuation of PFMT and/or pessary use, we will conduct a secondary analysis of compliers to estimate the effect of receiving the intervention as randomised, using complier average causal effect (CACE) estimators [37]. The CACE analysis will take a maximum likelihood approach, which can assume incomplete data to be missing at random, and can be adjusted for covariates. This analysis will provide unbiased effect estimates of receiving PFMT plus pessary (efficacy), which will complement the unbiased intention to treat effect estimates of being offered PFMT plus pessary (effectiveness). An "as treated" analysis will analyse participants on the basis of treatment received (Y/N).

Subgroup analyses will be carried out within the following groups: age (<52/≥52 years) and prolapse severity (POP-Q System: stage 0/1, stage 2, stage 3/4)). Stricter levels of statistical significance (1%) will be sought, reflecting the exploratory nature of these analyses. Heterogeneity of treatment effects amongst subgroups will be tested in an analysis of the 12-month outcome only (i.e. not a longitudinal model), using the appropriate subgroup by treatment group interactions [38].

Secondary outcomes will be analysed using an appropriate generalised linear model (for example, binary logistic regression for dichotomous outcomes such as improvement in prolapse stage (Y/N), and ordinal logistic regression for ordered categorical outcomes such as perception of global improvement (PGI-I)). All models will be adjusted for minimisation covariates (age, prolapse severity and centre) and baseline score (where applicable).

All analyses will be described in the Statistical Analysis Plan, to be approved by the TSC and DMEC. A single main analysis will be performed at the end of the trial when 12-month follow-up has been completed. The independent DMEC will review confidential interim analyses of accumulating data at its discretion but at least annually.

